#### 7.1.2.3 Other microbiological endpoints

Page 30 of 49

293Version: 1.0Status: ApprovedApproved Date:PTK0796-AP-17202Statistical Analysis Plan

Omadacycline (PTK 0796)

Paratek Pharma, LLC

PTK0796-AP-17202 Statistical Analysis Plan

Page 31 of 49

This copy of the document was retrieved from the system by 0.4/23/2020

93 Version: 1.0 Status: Approved Approved Date: PTK0796-AP-17202 Statistical Analysis Plan

Omadacycline (PTK 0796)

Paratek Pharma, LLC

PTK0796-AP-17202 Statistical Analysis Plan

#### 7.1.4 Modified Patient Symptom Assessment Questionnaire

The subject will report the severity of their pyelonephritis symptoms and how bothersome they are with the mPSAQ. The questionnaire will be completed during each study visit. The subject will rate the severity and how bothersome each symptom on a 4-point scale (no symptom, mild, moderate, severe and not at all, a little, moderately, a lot) and the results will be recorded in the eCRF. The investigator had to review the subject's responses and record any AEs as appropriate.

The mPSAQ is a self-administered, 6-item questionnaire that assesses the levels of 'severity' and 'bothersomeness' for each of the seven most frequently reported symptoms and signs of pyelonephritis symptoms:

Lower back pain or flank pain Chills, rigors or warmth Pain or uncomfortable pressure in the lower abdomen/pelvic area Pain or burning when passing urine Frequency of urination or going to the toilet very often

Urgency of urination or a strong and uncontrollable urge to pass urine

Each item has a Likert-type response scale, the 'severity' item response options being 'did not have', 'mild', 'moderate', 'severe', scored 0–3; and the bothersomeness item response options being 'not at all', 'a little', 'moderately', 'a lot', scored 0–3.

Total scores of the 6 items for the symptom severity scores and total scores for the 6 items related to the bothersomeness will be calculated for each subject and visit. The total scores for severity and bothersomeness will be between 0 and 18. The total score 0 is indicating the least severity of symptoms and a total score of 18 is indicating the worst symptom severity. For bothersomeness, the total score 0 is indicating the least bothersome score and a total score of 18 is indicating the most bothersome score.

93 Version: 1.0 Status: Approved Approved Date: PTK0796-AP-17202 Statistical Analysis Plan

Omadacycline (PTK 0796)

Paratek Pharma, LLC

PTK0796-AP-17202 Statistical Analysis Plan

For calculating the individual subject score by visit for both sub-scales the scores of non-missing item scores are summed up and divided by the number of non-missing items and then multiplied by 6. If less than 4 items are answered for each sub-scale, the total score is set to 'missing' for the sub-scale of the subject.

Total scores of the 6 items (Item 1 to 6) for the severity of symptoms scores and total scores for the 6 items related to the bothersomeness (Item 7 to 12) will be calculated.

Omadacycline (PTK 0796)

PTK0796-AP-17202 Statistical Analysis Plan

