### Appendix 3                      Modified Patient Symptom Assessment Questionnaire (mPSAQ)

Pyelonephritis Symptoms	Symptom Assessment	Bothersome Assessment
	Please indicate whether you have had the symptom in the past 24 hours?	If you have experienced the symptom in the past 24 hours, please indicate how bothersome they were?
Lower back pain or flank pain	No symptom	Not at all
	Mild	A little
	Moderate	Moderately
	Severe	A lot
Chills, rigors or warmth	No symptom	Not at all
	Mild	A little
	Moderate	Moderately
	Severe	A lot
Pain or uncomfortable pressure in the lower abdomen/pelvic area	No symptom	Not at all
	Mild	A little
	Moderate	Moderately
	Severe	A lot
Pain or burning when passing urine	No symptom	Not at all
	Mild	A little
	Moderate	Moderately
	Severe	A lot
Frequency of urination or going to the toilet very often	No symptom	Not at all
	Mild	A little
	Moderate	Moderately
	Severe	A lot

Omadacycline  
PTK0796-AP-17202-Version1.0; 26Mar2018

Paratek Pharma, LLC.  
IND # 75,928 IND # 73,431

Urgency of urination or a strong and uncontrollable urge to pass urine	No symptom	Not at all
	Mild	A little
	Moderate	Moderately
	Severe	A lot

Omadacycline  
PTK0796-AP-17202-Version1.0; 26Mar2018

Paratek Pharma, LLC.  
IND # 75,928 IND # 73,431

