- Prior and Concomitant Medication start date imputation will be imputed according to table in Appendix 4 Concomitant Medication Start Date Imputation.
- 2. Efficacy Data
- Analysis of efficacy data will be based on the available data, unless otherwise stated.
- Missing data for clinical and microbiological outcomes is denoted "indeterminate", unless any of the below rules apply.
- Missing microbiological outcomes at EOT will be imputed by last day of test article intake.
- The Overall Clinical Response at PTE and FFU visits are derived based on the "worst case scenario" to accommodate for missing visit assessments and intercurrent events (eg rescue

93 Version: 1.0 Status: Approved Approved Date: PTK0796-AP-17202 Statistical Analysis Plan

Omadacycline (PTK 0796)

Paratek Pharma, LLC

PTK0796-AP-17202 Statistical Analysis Plan

medication at EOT visit). Similar imputations were applied to microbiological response endpoints. Details are described in Section 7.

• mPSAQ data for bothersome score will be imputed with score of 0 for each question for which severity is answered "Did not have".

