#### 7.2.4 Sensitivity Analyses

#### 7.2.5 Modified Patient Symptom Assessment Questionnaire

Results of the mPSAQ questionnaire will be summarized in all populations.

Shifts from baseline will be summarized separately for symptom scores and bothersome scores at each post-Baseline assessment, daily up to EOT, PTE and at Final Follow-up.

Scores for symptoms and bothersomeness will be summarized by time point using descriptive statistics, for both the actual values and the change from baseline.

Omadacycline (PTK 0796)

PTK0796-AP-17202 Statistical Analysis Plan

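### The mPSAQ bothersomeness total fills a blank rating for a present symptom from items set to 0 for absent symptoms, so a symptomatic subject who gave no rating can score as least bothered

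*SAP*

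**What the plan says.** Protocol Appendix 3 lists six symptoms, each with a severity rating and a bother rating. The bother question is conditional: "If you have experienced the symptom in the past 24 hours, please indicate how bothersome they were". A symptom that is absent can therefore properly have no bother rating.

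SAP 5.3 handles that case: "mPSAQ data for bothersome score will be imputed with score of 0 for each question for which severity is answered" with the option meaning that the subject did not have the symptom.

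SAP 7.1.4 gives one scoring rule for both sub-scales: "the scores of non-missing item scores are summed up and divided by the number of non-missing items and then multiplied by 6". The safeguard is: "If less than 4 items are answered for each sub-scale, the total score is set to" missing. On range and meaning: "The total scores for severity and bothersomeness will be between 0 and 18", and "For bothersomeness, the total score 0 is indicating the least bothersome score and a total score of 18 is indicating the most bothersome score".

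SAP 7.2.5 states the use: "Scores for symptoms and bothersomeness will be summarized by time point using descriptive statistics", both as actual values and as change from baseline.

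The SAP does not say whether an imputed 0 counts as answered, and it has no rule for a symptom that is present but has no bother rating.

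**The concern.** Proration assumes that the items with a value stand in fairly for the blank one. For bothersomeness that assumption fails by construction. Once every absent symptom has been given a 0, a remaining blank belongs to a symptom that is present, unless its severity is blank too. The blank is then filled with an average that includes symptoms the subject does not have.

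The four-item minimum gives no protection, because four imputed zeros satisfy it when the subject has given no bother rating at all. Severity is not affected: it is asked for every symptom, so a 0 there is a real answer.

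At stake is one of the two mPSAQ sub-scale totals, summarised daily to end of treatment (EOT), at the post-therapy evaluation and at final follow-up. In relative terms the distortion is largest when few symptoms remain, so it would mostly affect later visits and could make improvement from baseline look greater than it was.

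**Working it through.** **Inputs.** Six items scored 0 to 3, the proration formula and the four-item minimum (SAP 7.1.4); bother set to 0 where the symptom is absent (SAP 5.3). Two assumptions: severity is complete, and imputed zeros count as answered.

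**Formula.** Let *a* symptoms be absent, *r* present and rated, and *b* present but blank, with a + r + b = 6. Let R be the sum of the ratings given. The SAP total is 6R/(a + r) if a + r ≥ 4, otherwise missing. At most two blanks are therefore possible in a scored record.

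**The plan's own range.** Six zeros give 0/6 × 6 = 0 and six threes give 18/6 × 6 = 18, which matches the stated 0 to 18.

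**Fully rated records.** With b = 0 the total is 6R/6 = R, which is correct.

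**No rating given.**
- Four absent, two severe and both unrated: 0/4 × 6 = 0. The severity total is 3 + 3 = 6. The true bother total lies between 0 and 6.
- Five absent, one unrated: 0/5 × 6 = 0. The true total lies between 0 and 3.

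**Some ratings given, each equal to 3.**

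| Absent / rated / blank | SAP total | Possible true total | True total if blanks are also 3 |
|---|---|---|---|
| 4 / 1 / 1 | 3/5 × 6 = 3.6 | 3 to 6 | 6 |
| 3 / 1 / 2 | 3/4 × 6 = 4.5 | 3 to 9 | 9 |
| 3 / 2 / 1 | 6/5 × 6 = 7.2 | 6 to 9 | 9 |
| 2 / 2 / 2 | 6/4 × 6 = 9.0 | 6 to 12 | 12 |
| 1 / 3 / 2 | 9/4 × 6 = 13.5 | 9 to 15 | 15 |

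**Ratio under equal bother.** With *s* symptoms present and *m* of them unrated, computed over true is 6(s − m)/((6 − m)s).
- s = 2, m = 1: 6/10 = 0.60
- s = 3, m = 1: 12/15 = 0.80
- s = 3, m = 2: 6/12 = 0.50
- s = 6: 1.0 for either m, since there are no imputed zeros

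**Direction without equal bother.** Four absent, one rated 3, one blank that was truly 0: the SAP total is 3.6 against a true 3. One absent, three rated 3, two blanks that were truly 1: the SAP total is 13.5 against 9 + 2 = 11. Both overstate.

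**Bound.** The SAP total is never below R, and with at most two blanks the true total is never above R + 6. The understatement is therefore at most 6 of 18 points.

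**The other reading of answered.** If imputed zeros do not count, the two zero-score cases above become missing. So does a symptom-free subject who left the bother items blank, and so does a subject with two symptoms both rated 3, whose correct total is 6.

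**The case against.** The strongest reply is that little depends on this score. SAP 7.1 makes all efficacy endpoints exploratory. The mPSAQ is summarised descriptively, and the bother total enters no clinical, microbiological or overall response and no planned posterior probability. The severity total would still show the symptoms that are present. This stands, and it limits the point to a scoring correction.

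Blanks may also be rare. The questionnaire is completed at study visits and the investigator must review the responses (Protocol 8.10). Automated checks look for missing data (Protocol 13.5.2), and queries are to be resolved before lock (Protocol 12.1). These controls make the problem less likely but do not exclude it, and the SAP keeps a proration rule because it expects some blanks.

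A reader might infer more than the documents support:
- *That blanks always lower the score unless all six symptoms are present.* This holds only under equal bother; the two overstated examples show the contrary. The score is certain not to overstate only when no present symptom is rated.
- *That no reading of the SAP gives correct totals.* If imputed zeros count, every record with all present symptoms rated is correct, including symptom-free subjects.
- *That cured subjects drop out of the by-visit means.* This needs the reading in which an imputed 0 is not answered. That reading would largely defeat the imputation in SAP 5.3, and the formula in 7.1.4 works on non-missing scores. It is unlikely, though one sentence should rule it out.
- *That the arms would be distorted differently.* Nothing in the documents shows this, and the trial is double-blind.

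**Conclusion.** The point holds for records in which a symptom is present and its bother rating is blank. Followed as written, SAP 5.3 and 7.1.4 can give the lowest possible bothersomeness total to a subject with two severe symptoms and no ratings. In partly rated records the total tends to be pulled toward 0.

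The understatement is at most 6 of 18 points for two unrated symptoms, and at most 3 when the only present symptom is unrated. The ratios rest on equal bother across present symptoms. All results assume that imputed zeros count as answered, which is the workable reading.

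How far the by-visit means would move cannot be computed, because the frequency of blanks is not stated. No response endpoint or treatment comparison is affected. It is worth correcting because the stated rule gives a wrong value and the severity data needed to put it right are already collected.

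**What to change.** Amend SAP 7.1.4 for bothersomeness only, before database lock:

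1. State that a bother item set to 0 because the symptom is absent counts as answered. A symptom-free subject then scores 0.
2. Replace a blank rating for a present symptom with the mean of that subject's rated present symptoms at the same visit.
3. Set the total to missing if fewer than half of the present symptoms are rated.
4. Where severity is blank too, presence is unknown: leave the item missing and keep the existing four-item minimum and proration. Without this clause, a subject with one rated symptom and five wholly blank items would pass step 3.

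Severity scoring stays as it is.

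In the examples, both zero-score cases become missing. Four absent, one rated 3 and one blank gives 6.0 in place of 3.6. Three absent, one rated and two blank becomes missing, since one of three is below half.

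A simpler rule, setting the total to missing whenever any present symptom is unrated, is also defensible but loses more records.

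The cost is SAP wording and one derivation step, with no new data and slightly more missing bother totals.

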# 7.2 Efficacy Endpoint Analysis

The efficacy endpoints include clinical response, microbiological response, and the composite of clinical and microbiological (overall) response, as measured by the number and percentage of subjects achieving success. The efficacy outcomes are measured by the number and percentage of subjects with successes in the ITT, micro-ITT populations, and other populations (CE and ME) as appropriate.

# 7.2.1 Investigator's Assessment of Clinical Success

The number and percentage of subjects with clinical success, failure, and indeterminate response as per investigator's assessment at the PTE visit in the ITT population will be determined by treatment group. Difference in success rates between levofloxacin and each omadacycline group will be provided. Point estimates will be provided together with the corresponding 95% confidence interval.

In addition, 95% credible intervals will be provided for the difference in success rates using the modeling as follows. Assuming the likelihood for number of responders to have binomial distribution  $[Y_i \sim Bin(n_i, p_i)]$  and non-informative beta priors  $[p_i \sim Beta(0.5, 0.5)]$ . The posterior probability of non-inferiority will be computed as  $P(p_{OMC} - p_L > -0.1 | data)$  for assessment.

Reason for investigator assessment of clinical failure and indeterminant at EOT, and for overall assessment at PTE and FFU visits will be tabulated for ITT, micro-ITT, and CE populations.

The analysis as described above will be repeated for EOT and FFU visits and provided also for CE and ME populations, as appropriate.

Overall clinical success at the PTE and EOT visits will be presented by pathogen and by pathogen and MIC for the micro-ITT and ME populations.

The analyses as described above will be repeated for pooled groups 2-4.

# 7.2.2 Microbiological Response Analysis

# 7.2.2.1 Per-Subject Microbiological Analysis

The per-subject microbiological (overall) response at the EOT and PTE Visits in the micro-ITT, ME-EOT and ME-PTE populations will be determined to support the clinical findings.

The number and percentage of subjects classified with a favorable (eradication and presumed eradication) and unfavorable (persistence, presumed persistence, and indeterminate) microbiological response (by definition, indeterminates are excluded from the ME population) will be tabulated for both treatment groups. Exact 95% CIs will be determined for the point estimates of the favorable microbiologic outcome rates in each treatment group.

Concordance of microbiological outcome with clinical outcome at EOT and PTE visits for micro-ITT and ME populations will be provided.

Number: GEN-STP-0293 Version: 1.0 Status: Approved Date: PTK0796-AP-17202 Statistical Analysis Plan

Omadacycline (PTK 0796)

Paratek Pharma, LLC

PTK0796-AP-17202 Statistical Analysis Plan

#### 7.2.4 Sensitivity Analyses

#### 7.2.5 Modified Patient Symptom Assessment Questionnaire

Results of the mPSAQ questionnaire will be summarized in all populations.

Shifts from baseline will be summarized separately for symptom scores and bothersome scores at each post-Baseline assessment, daily up to EOT, PTE and at Final Follow-up.

Scores for symptoms and bothersomeness will be summarized by time point using descriptive statistics, for both the actual values and the change from baseline.

Omadacycline (PTK 0796)

PTK0796-AP-17202 Statistical Analysis Plan

# 8 SAFETY ENDPOINTS AND ANALYSES

## 8.1 General

The safety population will be used for all safety analyses and safety summaries will be presented by treatment group.

## 8.2 Duration of Exposure to Test Article and Compliance

Exposure summary by treatment group and separately by route of administration (iv, po) will be presented for the Safety and micro-ITT populations.

The distribution of subjects by the total number of days on therapy (0, 1, 2-3, 4-6, 7-10, 11-14, and > 14 days), the number of days on iv infusion and the number of days of oral test article will be presented.

A summary of the number of days of iv therapy prior to oral switch defined as 24-hour periods (ie, time to oral switch), the day of oral switch, and the criteria for iv to oral switch will be presented by treatment group. For the Safety population, the summary of test article exposure will be based on the actual treatment received whereas for all other analysis sets, the summary will be based on the randomized treatment.

Treatment compliance is defined as the number of iv doses (including partial doses, active and placebo) and oral

% Compliance =  $100\% * \frac{number of doses actually received}{number of doses expected to received}$ 

The number of dosed expected to be received by the patient will be calculated over the time period defined by the first infusion date and the last dose date.

All oral doses should be taken in a fasted state. Fasting is defined as no food, antacids or multivitamins containing multivalent cations (eg, aluminum, magnesium, calcium, bismuth, iron, or zinc) or drink except water for at least 6 hours before dosing. After dosing, no food is permitted for 2 hours as well as no dairy products, antacids or multivitamins containing multivalent cations (eg, aluminum, magnesium, calcium, bismuth, iron, or zinc) for 4 hours.

Number of subjects and percentage with a compliance  $\geq 80\%$  will be presented. A summary of compliance to oral test article intake with the pre and post-dose fasting requirements will also be provided for subjects switching to oral administration. The percent fasting compliance will be determined based on the total doses taken for days the subjects were on po medication. The percentage of subjects who were < 50\%, 50% to < 80%, and 80% to 100% compliance with the pre-dose and post-dose fasting requirements met will be summarized.

Omadacycline (PTK 0796)

PTK0796-AP-17202 Statistical Analysis Plan

## 8.3 Concomitant Medications

Medications will be coded by WHODRUG Anatomical Therapeutic Chemical Classification (ATC) level 3 and generic medication name. Treatments that have been administered within 7 days prior to the date of informed consent until the end of study are recorded in the eCRF.

Medications are considered concomitant if taken on or after the first dose of test article, or if their stop date is unknown or marked as continuing. Thus, in cases where a medication starts prior to the first dose, and continues throughout the treatment period, the medication will be summarized as both prior and concomitant. Subjects will be counted only once for an ATC class and generic medication name.

All medications and significant non-drug therapies (including physical therapy and blood transfusions) administered after the subject starts treatment with test article will be listed.

## 8.4 Adverse Events

Adverse events (AEs) will be recorded and reported from signing of the ICF to the end of study. AEs will be coded using the MedDRA to the SOC and PT levels.

A treatment-emergent AE is defined as any AE that newly appeared or worsened in severity on or after the initiation of test article. An AE is considered treatment emergent if the AE start date and time is on or after the start date and time of the first dose of test article.

Summary tables will be provided for all treatment-emergent adverse events (TEAEs).

An overall summary of AEs will include the number of subjects who experienced at least one AE of the following categories: any AE, any TEAE, any drug-related TEAE, any severe TEAE, any serious TEAE, any drug-related serious adverse event, any serious TEAE leading to death, any TEAE leading to premature discontinuation of test article and any TEAE leading to premature discontinuation from study, and any serious TEAE leading to premature discontinuation of test article.

The number and percentage of subjects reporting a TEAE in each treatment group will be tabulated by SOC and PT. The incidence of serious TEAEs, TEAEs judged to be related to test article, TEAE leading to premature discontinuation of test article and from study will be summarized by SOC and PT. Additionally, a summary by SOC, PT, and severity (mild, moderate, and severe) will be provided. For all analyses of TEAEs, if the same AE (based on PT) is reported for the same subject more than once, the AE is counted only once for that PT and at the highest severity and strongest relationship to test article.

For the two omadacycline dose groups and the levofloxacin treatment group with the possibility to switch from iv to oral test article AEs will be summarized by incidence of subjects with events starting during iv treatment and events starting after the switch to oral treatment and combined for the total treatment group. This summary will be presented by SOC and PTs.

93 Version: 1.0 Status: Approved Approved Date: PTK0796-AP-17202 Statistical Analysis Plan

Omadacycline (PTK 0796)

Paratek Pharma, LLC

PTK0796-AP-17202 Statistical Analysis Plan

In addition, all AEs (including non-TEAEs), serious TEAEs, and TEAEs leading to discontinuation of test article will be provided in listings by treatment group, study site, subject, verbatim term, MedDRA SOC and PT, start and end date, seriousness flag, severity, relationship to test article, relationship to study protocol, action taken with test article, non-test article action taken and outcome.

For subjects with a TEAE of nausea or vomiting (based on the MedDRA PT), the total number of nausea and vomiting events, descriptive statistics of the study day of first onset of these events, and descriptive statistics for the duration (in days) of events, will be presented by treatment group.

Listings of hospitalizations will be provided.

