Study PTK0796-UUTI-15103 was a randomized (1:1:1), open-label, parallel-designed Phase 1b study evaluating 3 dosing regimens of omadacycline in 31 female adults with cystitis. During the treatment period, serial blood and urine samples were collected for safety, microbiological, and pharmacokinetic (PK) analyses of omadacycline. In this study, the PK of omadacycline in women with cystitis was found to be similar to the PK in healthy subjects. At steady-state, 10% to 13% of a po omadacycline dose is excreted in the urine, resulting in high urine concentrations. With the treatment regimens studied, observed urine concentrations of omadacycline compared favorably with MIC values for common UTI pathogens, and a high percentage of subjects achieved clinical success and favorable microbiological responses. There was a higher than expected incidence of nausea and vomiting, which contrasts with the notably lower rates of nausea and vomiting observed in other omadacycline studies using comparable dosing regimens and active controls. The reason(s) for the increased incidences in nausea and vomiting are difficult to ascertain given the open-label study design, small sample size, and lack of prior experience with omadacycline in the UTI study population.

This study is intended to evaluate the efficacy and safety of iv/po omadacycline as compared to iv/po levofloxacin in the treatment of adult subjects with AP. This data will be important to determine the potential utility of omadacycline for the treatment of UTI and will help in selection of dosing regimens that may be used in future UTI studies.

It is expected that the dosing regimens evaluated in this study will provide urine concentrations of omadacycline that will exceed the MIC90 for the common AP pathogens (see dose selection discussion in [Section 7.4](#)).

Please refer to the current version of the Investigator's Brochure for additional information on omadacycline.

Omadacycline  
PTK0796-AP-17202-Version 1.0; 26Mar2018

Paratek Pharma, LLC.  
IND # 75,928 IND # 73,431

---

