#### 7.6.5 Investigator's Decision to Switch from iv to po Treatment

Initially, all randomized subjects will receive at least 1 day of iv antibacterial therapy. Beginning on the day 2 visit, the subject may be eligible to switch from iv to po therapy.

Switch from active iv to active po study drug therapy is optional, and will occur based on treatment group assigned. Upon decision to switch, subjects randomized to iv only groups will begin to receive placebo po in addition to their active iv test article. Those in an iv/po group will begin to receive active po test article and placebo iv infusions. The decision should be made by the investigator based on evaluation of the criteria below. Criteria will be confirmed and documented in source documents:

- Afebrile for  $\geq 24$  hours (highest daily oral, tympanic, rectal, or core temperature  $< 37.8^{\circ}\text{C}$  [ $100.0^{\circ}\text{F}$ ]) without the use of anti-pyretics,
- Improvement or resolution of the signs and symptoms of the index AP,
- Ability to tolerate and ingest oral therapy (eg, no nausea, vomiting), and
- For subjects with baseline bacteremia, follow-up blood cultures must be negative.

Subjects who are switched to po test article administration will continue to receive iv infusions in order to maintain the blind. Switch to po will not be permitted until after the subject has completed at least the first day of iv treatment (after 1 dose). The date and time the investigator confirmed the criteria for the subject's eligibility for po treatment were met and made the decision to switch to po treatment will be recorded on source documents and the information transferred to eCRFs by study site personnel.

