#### 7.6.6 Oral Treatment Phase

When switching from iv to po test article the recommended interval between doses will be maintained. The first po dose, for both omadacycline and levofloxacin treatment arms, should be given in the morning 12 to 24 hours after the last dose of iv test article.

The po treatment phase will employ a double-blind, double-dummy design using omadacycline placebo comparator tablets of matching size and shape to active omadacycline tablets and matching over-encapsulated placebo and active levofloxacin tablets.

To maintain investigator and subject blinding, subjects in both arms will receive both tablets and over-encapsulated tablets during each dose. Subjects in groups 1 and 2 will receive placebo omadacycline tablets and placebo over encapsulated levofloxacin tablets. Subjects in groups 3, 4 and 5 will also continue to receive iv placebo infusions to maintain the blind.

The po treatment will be administered by study staff during visit assessments.

All doses of oral test article should be taken with water.

All oral doses should be taken in a fasted state. Fasting is defined as no food, antacids or multivitamins containing multivalent cations (eg, aluminum, magnesium, calcium, bismuth, iron, or zinc) or drink except water for at least 6 hours before dosing. After dosing, no food is permitted for 2 hours as well as no dairy products, antacids or multivitamins containing multivalent cations (eg, aluminum, magnesium, calcium, bismuth, iron, or zinc) for 4 hours.

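### The adverse event table split at the iv-to-oral switch omits the iv-only omadacycline arms, whose blinded dummy switch is the comparator needed to read it

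*SAP*

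**What the plan says.** SAP 8.4 plans one adverse event summary by treatment phase. It applies "For the two omadacycline dose groups and the levofloxacin treatment group with the possibility to switch from iv to oral test article" and reports "events starting during iv treatment and events starting after the switch to oral treatment and combined for the total treatment group". Under Table 1 of either document, the arms with a real oral option are Groups 3 and 4 (omadacycline) and Group 5 (levofloxacin).

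Groups 1 and 2 are also switched, in the blinded sense. Protocol 7.6.5 states: "Upon decision to switch, subjects randomized to iv only groups will begin to receive placebo po in addition to their active iv test article". Protocol 7.6.6 adds: "Subjects in groups 1 and 2 will receive placebo omadacycline tablets and placebo over encapsulated levofloxacin tablets". Protocol Table 2 gives every group the same oral load after the switch: three tablets and three over-encapsulated tablets.

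The timing of the switch is captured. Protocol 7.6.5 says that the date and time at which the investigator confirmed the criteria and "made the decision to switch to po treatment will be recorded on source documents and the information transferred to eCRFs by study site personnel", and does not limit this to the arms with active oral drug. SAP 8.2 already promises that "the day of oral switch, and the criteria for iv to oral switch will be presented by treatment group".

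For all arms, SAP 8.4 also gives overall tables of treatment-emergent events, listings with start dates, and the number, first-onset day and duration of nausea and vomiting events. None of these is split at the switch, and neither document has a phase table for Groups 1 and 2.

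**The concern.** A reader will naturally take an iv column beside an after-switch column as evidence on how well the oral drug is tolerated. Within Groups 3 to 5 three other things change at the same moment:

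- **Time.** The oral phase always comes later in the illness.
- **Time at risk.** Events are collected to the end of the study, and the after-switch phase has no stated end. The two phases can differ greatly in length, yet the table reports crude incidence.
- **Selection.** Protocol 7.6.5 requires the subject to be afebrile, improving and able to take oral therapy, with absence of nausea and vomiting given as the example. The after-switch column starts from subjects chosen partly on the events of interest.

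Nausea and vomiting are listed as events of interest in the synopsis. Of the earlier Phase 1b cystitis study, Protocol 3.2 reports: "There was a higher than expected incidence of nausea and vomiting". It says the cause was hard to establish, in part because that study was open-label. The present trial is blinded and contains an omadacycline arm that takes dummy tablets under the same switch rules. The planned table leaves it out.

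**Working it through.** The plan states no figure for this table, so there is none to reproduce. The check has three parts.

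**1. Which arm is a suitable comparator (Protocol Table 1 and Table 2)**

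| Group | Day 1 | From Day 2, before switch | After switch |
|---|---|---|---|
| 1 | 200 mg iv | 200 mg iv | 200 mg iv + placebo tablets |
| 2 | 200 mg iv | 100 mg iv | 100 mg iv + placebo tablets |
| 3 | 200 mg iv | 100 mg iv | 300 mg oral + placebo iv |
| 4 | 200 mg iv | 100 mg iv | 450 mg oral + placebo iv |

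Groups 2, 3 and 4 are treated identically up to the switch, and the switch decision is blinded, so those who switch should be comparable at that moment. Group 1 has a different iv dose from Day 2. Comparing it with Groups 3 and 4 would mix dose with route, and the dose could also affect who qualifies to switch.

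**2. What the split shows when route has no effect**

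The documents give no event rates, so all hazards here are assumed.

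Constant hazard h per day on both routes: incidence in a phase of d days = 1 − exp(−h·d). Take h = 0.02 and first oral dose on Day 3, so that there are 2 iv days.

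- During iv: 1 − exp(−0.02 × 2) = 3.9%
- After switch to Day 10: 1 − exp(−0.02 × 8) = 14.8%
- After switch to Day 28: 1 − exp(−0.02 × 26) = 40.5%

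For h from 0.01 to 0.04 and first oral dose on Day 2, 3 or 5, the ranges are 1.0–14.8% during iv, 5.8–30.2% after switch to Day 10, and 21.3–66.0% to Day 28.

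Falling hazard (8% on Day 1, halving every 2 days), first oral dose on Day 5:

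- During iv: the four daily hazards sum to 0.080 + 0.057 + 0.040 + 0.028 = 0.205, giving 1 − exp(−0.205) = 18.5%
- After switch to Day 10: the six daily hazards sum to about 0.060, giving 5.8%

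The direction of the contrast reverses although route does nothing in either case.

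**3. Precision once Group 2 is added**

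Planned size per arm at equal allocation: 200 / 5 = 40. For a common event rate p and n switchers per arm, the 95% half-width is 1.96·√(2p(1−p)/n). With p = 0.20 (assumed):

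- All switch, n = 40: 1.96·√(0.32/40) = 17.5 points for Group 3 or 4 against Group 2
- 60% switch (assumed), n = 24: 1.96·√(0.32/24) = 22.6 points

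Pooling Groups 3 and 4 against Group 2 uses 1.96·√(p(1−p)(1/n + 1/(2n))), which gives 15.2 and 19.6 points.

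**The case against.** The strongest reply is that the trial already plans a cleaner comparison. Groups 2, 3 and 4 differ only from the switch onward, and SAP 8.4 tabulates treatment-emergent events for every group. Group 2 against Groups 3 and 4 in that table compares arms as randomized, with no conditioning on a later decision. This stands. That comparison is diluted by the shared iv days, however, and does not isolate the period after the switch. The nausea and vomiting onset summaries and the listings help, but are not split at the switch either.

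A second reply is that levofloxacin is in the phase table, takes the same number of tablets and follows the same switch rules. It gives some control for time and tablet burden. But it is a different drug and changes route itself.

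Three stronger readings are tempting and are not supported:

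- **That 300 mg and 450 mg cannot be compared after the switch.** They can. Groups 3 and 4 are both in the planned table, with the same iv regimen, criteria and oral load.
- **That about 80 of 200 subjects form an omitted randomized control.** Only Group 2 is a clean comparator, about 40 subjects at equal allocation and fewer once non-switchers are removed. The comparison uses subjects selected by a decision made after randomization.
- **That oral tolerability was a main reason for four regimens.** No section says so. The dose rationale in Protocol 7.4 is to find iv and oral doses with clinical success similar to a standard comparator.

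**Conclusion.** The point holds as a limited one about a descriptive safety table. As planned, the phase split in Groups 3 to 5 is confounded with time, time at risk and selection. It cannot show whether events after the switch are due to oral omadacycline, to the course of the illness or to the tablets. The comparator that would help is already in the trial, and its switch times appear to be recorded.

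Even with Group 2 shown, the contrast is active oral drug against continued active iv plus placebo tablets, not drug against no drug. It depends on the blind holding when the switch is decided and, if arms are dropped or ratios change, on comparing subjects randomized concurrently. Levofloxacin has no iv-only arm, so its route effect cannot be isolated in this way. The precision in the working assumes that equal allocation persists. Efficacy conclusions do not depend on this table, and making the change is desirable rather than essential.

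**What to change.** In SAP 8.4, present the phase table for all five groups, split at each subject's recorded switch date and time, active or dummy, using the same anchor in every group. Give the number of subjects who switched in each group, and either subject-days per phase or a fixed after-switch window. Display Group 2 beside Groups 3 and 4 as the descriptive comparator. Show Group 1 in its own column rather than pooled with Group 2.

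Add a note stating that:

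- the contrast is active oral against continued active iv plus placebo tablets;
- it is limited to subjects who switched, which is a blinded decision after randomization;
- it should use concurrently randomized subjects if arms or ratios change;
- its precision is modest.

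The cost is two more columns, a time-at-risk line and a note in one table. No further data collection appears necessary, since the protocol sends the switch date and time to the eCRF without restricting this by arm.
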